5.3 Lifestyle Considerations

Participants are recommended to continue to use sunblock.

5.3.1 Meals and Dietary Restrictions

No food restrictions. On scheduled study visit days with PK assessment (see Table 1), record the date and time of the closest meal before and after the study-drug administration.

5.3.2 Activity

Participants will abstain from strenuous exercise for 24 hours before each blood collection for clinical laboratory tests. Participants may participate in light recreational activities (e.g., watching television, or reading).

5.4 Screen Failures

Retesting:

During the initial Screening Period or single rescreening period, testing may be repeated once for participants if test results would preclude enrollment in the study and are thought to represent a laboratory error, or a reversible, clinically insignificant intermittent condition, or are inconsistent with the subject's historical values. When a laboratory test needs to be repeated during the Screening Period, or to accommodate other unanticipated events, the Screening Period may be extended to 7 weeks after discussion with the Medical Monitor.

Rescreening:

Individuals who do not meet the criteria for participation in this study (screen failure) may be rescreened once, after approval by the Medical Monitor. Rescreened participants will be assigned a new participant number.

If a participant is rescreened, all Screening tests should be repeated with the exception of:

- Hepatitis and HIV testing must have occurred within 1 month of the initial Rescreening Visit or will need to be repeated during the Rescreening Period.
- Anti-ENA antibodies (anti Sm, RNP, Ro/SSA, La/SSB Abs) must have occurred within 1 month of the initial Rescreening Visit or will need to be repeated during the Rescreening Period.
- Documented TB testing must have occurred within 3 months of the initial Rescreening Visit or need to be repeated during the Rescreening Period.
- Documented chest imaging must have occurred within 3 months of the Rescreening Period otherwise to be repeated during the Rescreening Period.

If inclusion/exclusion criteria are not met based on the results of the repeated testing, the participant should be considered a screen failure and not enrolled in the study. Reasons for screening failure should be recorded in the eCRF.

6 Study Intervention and Concomitant Therapies

Study intervention is any investigational intervention(s), marketed product(s), placebo, or medical device(s) intended to be administered to a study participant per the study protocol.

6.1 Study Intervention Administration

Participants will self-administer study intervention twice per day (every 12 hours \pm 2 hours) (see Section 1.3). To maintain blinding, all participants will take 4 tablets in total per dose administration (4 tablets in the morning and 4 tablets in the evening): 25 mg enpatoran tablets and/or matching placebo, depending on the assigned dose level, as described in Table 3. In case of adaptation to include a 150 mg dose level (see Section 4.3), 50 mg enpatoran tablets and/or matching placebo tablets will be used for Cohort B Part 2 participants enrolled after this implementation: these participants would take, 3 tablets in total per dose administration (3 tablets in the morning and 3 tablets in the evening). Table 3 describes the enpatoran and/or placebo tablets count per dose level. No dose modification is allowed for Cohort B participants randomized before dose adaptation (see Section 6.5).

On scheduled study visit days, the participant will be asked not to self-administer study intervention at home but to bring the study intervention to the site for administration after the scheduled study visit assessment/procedures are performed (other than post-treatment ECGs and PK/PD sampling). Last study intervention will be administered prior to the End of Treatment Visit of the 24-Week DBPC period for those who opt out for the separate WILLOW LTE Study.

 Table 3
 Study Intervention Administration

Study Intervention Name	Enpatoran	Placebo
Dose Formulation:	Film-coated tablet. All formulation components are of pharmacopoeial and/or food grade.	Film-coated tablet. All formulation components are of pharmacopoeial and/or food grade.
Unit Dose Strengths	25 mg or 50 mg	Matching active 25 mg or 50 mg tablets
Dosage Levels:	25 mg, 50 mg, 100 mg or 150 mg	Not applicable.
Route of Administration:	Oral	Oral
Packaging and Labeling:	Study Intervention will be provided in wallets containing 24 units (for 25 mg tablets) or 18 units (for 50 mg tablets) in Alu/Alu blister. Each wallet will be labeled per country requirement and Good Manufacturing Practice Guidelines.	Study Intervention will be provided in wallets containing 24 units (for 25 mg tablets) or 18 units (for 50 mg tablets) in Alu/Alu blister. Each wallet will be labeled per country requirement and Good Manufacturing Practice Guidelines.

Dosing Instructions:

- Oral twice per day administration. To be taken with approximately 200 mL water
- No specific food restriction. On scheduled study visit days with PK assessment, record the date, and time of the closest meal before and after the study-drug administration.

All participants randomized to enpatoran arms:

For 25 mg Tablets:

- For 25 mg dose: 1 × 25 mg enpatoran tablet + 3 × placebo tablets (twice per day)
- For 50 mg dose: 2 × 25 mg enpatoran tablets + 2 × placebo tablets (twice per day)
- For 100 mg dose: 4 × 25 mg enpatoran tablets (twice per day)

For 50 mg Tablets:

- For 50 mg dose: 1 × 50 mg enpatoran tablet + 2 × placebo tablets (twice per day)
- For 100 mg dose: 2 × 50 mg enpatoran tablets + 1 × placebo tablets (twice per day)
- For 150 mg dose: 3 × 50 mg enpatoran tablets (twice per day)

All participants randomized to placebo arm:

For 25 mg Tablets:

• 4 placebo tablets (twice per day)

For 50 mg Tablets:

• 3 placebo tablets (twice per day)

6.2 Study Intervention Preparation, Handling, Storage, and Accountability

Enpatoran and placebo will be provided in tablet formulation in an Alu/Alu blister package (see Section 6.1) and it has to be stored at $\leq 30^{\circ}$ C (should not be frozen).

Packaging and labeling of enpatoran and placebo tablets will be in accordance with applicable regulatory requirements and applicable Good Manufacturing Practice guidelines. The information on the medication will be in accordance with approved submission documents. Enpatoran and placebo tablets will be packed and labeled to protect the blinded nature of the study. Enpatoran and placebo will not be distinguishable from each other and will be covered by suitable labels to prevent participants and study personnel from noticing any differences in the tablets of enpatoran versus placebo. Blinded treatment kit numbers will be obtained through the IVRS/IWRS as described in Section 6.3.

• The Investigator, institution, or the head of the medical institution (where applicable) is responsible for study intervention accountability, reconciliation, and record maintenance (i.e., receipt, reconciliation, and final disposition records).

Upon receipt of the study interventions, the Investigator or designee will confirm appropriate temperature conditions have been maintained during transit and any discrepancies are reported and resolved before use. Also, the responsible person will check for accurate delivery. Further

guidance and information for study intervention accountability are provided in the Pharmacy Manual.

- Only participants enrolled in the study may receive study interventions and only authorized site staff may supply it. All study interventions will be stored in a secure, environmentally controlled, and monitored (manual or automated) area, per the labeled storage conditions, and with access limited to the Investigator and authorized site staff.
- Dispensing will be recorded on the appropriate accountability forms so that accurate records will be available for verification at each monitoring visit.
- Study interventions accountability records at the study site will include the following:
 - Confirmation of receipt, in good condition, and in the defined temperature range.
 - The inventory provided for the clinical study.
 - The doses each participant used during the study.
 - The disposition (including return, if applicable) of any unused study interventions.
 - Dates, quantities, batch numbers, blister package numbers, expiry dates of study interventions, and the participant numbers.
- The Investigator site will maintain records, which adequately documents that participants were provided the doses specified in this protocol, and all study interventions provided were fully reconciled.
- Unused study interventions will not be discarded or used for any purpose other than the present study. There will be the option that unused study interventions will be redispensed to the same patient controlled by IRT. No study intervention that is dispensed to a participant may be redispensed to a different participant.
- A Study Monitor will periodically collect the study interventions accountability forms.
- Further guidance and information for the final disposition of unused study interventions are provided in the Pharmacy Manual.

Participants will record date, time, and amount of study intervention administration in the paper diary card provided.

6.3 Measures to Minimize Bias: Study Intervention Assignment and Blinding

6.3.1 Study Intervention Assignment

After confirmation of participant eligibility, study participants in each cohort will be centrally allocated to study intervention using an IVRS/IWRS and per a computer-generated randomization list:

• In Cohort A, the randomization ratio will be 1:1:1:1 ratio (enpatoran 25 mg twice per day: enpatoran 50 mg twice per day: enpatoran 100 mg twice per day: placebo) and the number of study participants randomly assigned to study intervention will be approximately 100.

- In Cohort B, the Part 1 participants will be assigned with a 2:1 ratio (enpatoran 100 mg twice per day: placebo). Part 2 participants will be assigned with a 1:1:1:1 ratio (enpatoran 25 mg twice per day: enpatoran 50 mg twice per day: enpatoran 100 mg twice per day: placebo. Part 2 dose levels and randomization ratio might be adapted after Cohort B IA.
- The IVRS/IWRS will be used to assign unique participant numbers, allocate participants to study intervention group at the Randomization Visit in DBPC treatment period, and allocate study intervention to participants at each study intervention visit.

Before the study is initiated, the telephone number and call-in directions for the IVRS and/or the log in information and directions for the IWRS will be provided to each site. The site will contact the IVRS/IWRS prior to starting study intervention administration for each participant.

Participants in Cohort A will be stratified by the following factors:

- Region (3 levels: North America and Western Europe vs Asia vs Central/South America and rest of the world),
- Disease diagnosis at Screening (2 levels: CLE [SCLE and/or DLE] vs SLE).

Participants in Cohort B will be stratified by the following factors (not all stratification factors might be used after Cohort B IA, as will be specified in the Interim Analysis Plan):

• Region (3 levels: North America and Western Europe vs Asia vs Central/South America and rest of the world),

6.3.2 Blinding

Blinding Method

The study will be double-blind for Cohort A and Cohort B (Parts 1 and 2).

Randomization codes will be kept strictly confidential, accessible only to authorized staff (i.e., randomization statistician, unblinded Statistician, IDMC members, and statistical data centers, Firewall Team, unblinded Pharmacist, and laboratories responsible for analyses of the PK), until the time of unblinding. All other study-related individuals, ancillary site staff, clinical research associates/monitors, the Investigator, Sponsor, and clinical research organization staff will remain blinded to study intervention.

The analytical laboratories responsible for the analysis of the PK samples (requiring shipment of laboratory samples from the site) will be unblinded to study treatment codes to enable sample testing of PK of study intervention prior to database lock. Masked participant identifiers will be used to support association with treatment codes but prevent association of treatment codes with any other clinical data, such as safety, and clinical response data.

The EAC will be blinded to treatment. Blinded efficacy and safety data will be provided to the EAC for data monitoring (for more details see Appendix 2).

The IDMC and supporting independent statistical data centers will be unblinded to treatment.

In addition, the IDMC will present recommendations based on the results of the IAs to the Firewall Team to make final decision (see Section 9.4.4). The Firewall Team will be unblinded to treatment and will remain independent from study team. Details will be provided in the Firewall Team charter.

For the primary analysis and final analysis, database should be locked, and protocol violations determined, the drug codes will be broken and made available for data analysis.

Study intervention information that would unblind the study participants will not be reported with participant identifiers to investigative sites until after the study has been fully unblinded (i.e., after the final analysis).

Assignment Method Retention

The study blind may be broken in the event emergency unblinding is necessary for participant safety or the reporting of SUSARs.

Unblinding in these cases would be done via the unblinding module in IWRS. All breaks of the study blind must be adequately documented.

6.3.3 Emergency Unblinding

In an emergency, the Investigator is solely responsible for determining if unblinding of a participant's study intervention assignment is warranted. Participant safety is always the first consideration in this decision. If the Investigator decides that unblinding is warranted, the Investigator makes every effort to contact the Sponsor prior to the unblinding, unless this could delay emergency treatment. The Sponsor will be notified within 24 hours after unblinding. The Investigator will provide the Sponsor the reason for unblinding without revealing the study intervention, except to the designated global patient safety representative via the Emergency Unblinding Notification Form. The date of and reason for unblinding will be recorded in the source documents. Contact information for unblinding in an emergency is given on the participant emergency card provided to each participant, as noted in Appendix 2.

The Sponsor's global patient safety department will submit any SUSAR reports to regulatory authorities and ethics committees with unblinded information, per applicable regulations. Only blinded information will be provided to the study team.

Participants undergoing emergency unblinding will be discontinued from the study intervention. The investigations scheduled for the ET and all subsequent Safety Follow-up Visits until EOS should be performed (Section 7.1).

6.4 Study Intervention Compliance

Besides study visits where study intervention will be administered under medical supervision at the site, study participants will self-administer their study intervention at home. They will be provided with a diary card or phone application containing instructions for self-administration and documentation of study intervention intake. If participants use the phone application, they may also receive reminders to administer study intervention and perform related documentation.

When participants self-administer study interventions at home (see Section 1.2), compliance with study intervention will be assessed at each visit. Compliance will be assessed by direct questioning, counting returned tablets, and review of diary cards or data generated from the phone application using the vendors portal and documented in the source documents and CRF. Any deviation(s) from the prescribed dosage regimen are recorded.

When participants are dosed at the site, they will receive study intervention directly from the Investigator or designee, under medical supervision. The date and time of each dose administered in the clinic will be recorded in the source documents and recorded in the CRF. The dose of study intervention and study participant identification may be confirmed at the time of dosing by a member of the study site staff other than the person administering the study intervention.

A record of the number of tablets dispensed to and taken by each participant will be maintained and reconciled with study intervention and compliance records. Intervention start and stop dates, including dates for intervention delays will also be recorded in the CRF.

6.5 Dose Selection and Modification

- Participants enrolled into Cohort A will be randomized in a 1:1:1:1 ratio receiving placebo or one of the 3 active doses, i.e., 25, 50, or 100 mg of enpatoran, twice daily while patients enrolled into Cohort B (SLE) Part 1 will be randomized in a 2:1 ratio receiving either 100 mg enpatoran or placebo twice daily for a treatment duration of at least 24 weeks.
- In Cohort B Part 2, participants will start with a randomization ratio of 1:1:1:1 receiving placebo or one of the 3 active dose levels, i.e., 25, 50, or 100 mg of enpatoran, twice daily. After Cohort B IA, Part 2 dose levels (not exceeding the highest clinically investigated enpatoran dose in the ongoing Phase 1b study: MS200569_0004 which is 150 mg twice per day), randomization ratio and stratification, and sample size may be adapted.
- Participants from Cohort B Part 1 and Part 2 will continue on their dose level initiated prior
 to any potential adaptation until completion of study treatment at Week 24 unless Cohort B
 is terminated for futility. Dose adaptations, if any, will be implemented only for new
 Cohort B Part 2 participants enrolled after this decision is made.

6.6 Continued Access to Study Intervention After the End of the Study

Participants who complete the 24-Week DBPC Treatment Period may be offered participation in an optional LTE study (WILLOW LTE, MS200569_0048).

6.7 Treatment of Overdose

For this study, any dose of study intervention greater than 300 mg (12 tablets) within 24 hours \pm 2 hours or a single-dose greater than 200 mg (8 tablets) will be considered an overdose.

The Sponsor has no specific recommendation for treating an overdose. The Investigator will use his/her clinical judgment to manage any overdose, considering the symptoms, and any site procedures or standards.

Even if not associated with an AE or a SAE, any overdose is recorded in the CRF and reported to global patient safety in an expedited manner. Overdoses are reported on a SAE and Overdose Report Form, following the procedure in Appendix 4.

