is expected to generate similar exposures as 2 tablets of 25 mg strengths. The 50 mg tablet strengths may be introduced into Cohort B Part 2 to facilitate doses from 50 to 150 mg.

Based on the above considerations, the proposed enpatoran doses in this Phase 2 study should provide the opportunity to evaluate a treatment effect and dose-exposure-response relationships for efficacy and safety in each indication, SLE, and CLE, with acceptable safety margins. Refer to the IB for further details.

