- Anticipated day-to-day fluctuations of pre-existing disease(s) or condition(s) present or detected at the start of the study that do not worsen.

Other Adverse Events to be Reported Using a Specialized Procedure or Form

- All pregnancies occurring during the study and their outcome will be documented on the Pregnancy report form and Parent-Child/Fetus Adverse Event Report form as outlined in Section 8.3.4.
- The following procedures should be followed for reporting overdoses (refer to CRF guidelines for further details):
 - Overdoses without an AE should be reported using the paper SAE Overdose Report form only, stating if the overdose was accidental or intentional.
 - Overdoses associated with a non-serious AE must be recorded on the AE CRF and also the paper SAE Overdose Report form. Overdoses associated with an SAE must be recorded on the AE CRF and the paper SAE Report form.

SAE Definition

If an event is not an AE per the definition above, then it cannot be an SAE even if serious conditions are met (e.g., hospitalization for signs/symptoms of the disease under study, death due to progression of disease).

A SAE is defined as any untoward medical occurrence that, at any dose:

a. Results in death

b. Is life-threatening

The term 'life-threatening' in the definition of 'serious' refers to an event in which the participant was at risk of death at the time of the event. It does not refer to an event, which hypothetically might have caused death, if it were more severe.

c. Requires inpatient hospitalization or prolongation of existing hospitalization

- In general, hospitalization signifies that the participant has been detained (usually involving at least an overnight stay) at the hospital or emergency ward for observation and/or treatment that would not have been appropriate in the physician's office or outpatient setting. Complications that occur during hospitalization are AEs. If a complication prolongs hospitalization or fulfils any other serious criteria, the event is serious. When in doubt as to whether "hospitalization" occurred or was necessary, the AE is to be considered serious.
- Hospitalization for elective treatment of a pre-existing condition that did not worsen from Baseline is not considered an AE.

• However, all events leading to unplanned hospitalizations or unplanned prolongation of an elective hospitalization must be documented and reported as SAEs.

d. Results in persistent disability/incapacity

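### The overdose tablet counts in Protocol 6.7 (12 and 8) fit 25 mg tablets only; with the optional 50 mg tablets in a 150 mg BID arm they equal 600 and 400 mg, twice the printed limits

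*Protocol*

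**What the plan says.** Protocol 6.7 sets one overdose rule for the whole study. It has two limbs: "any dose of study intervention greater than 300 mg (12 tablets) within 24 hours" (with a 2-hour tolerance on the window), and "a single-dose greater than 200 mg (8 tablets) will be considered an overdose". Tablet strength is not mentioned. The same section requires that "any overdose is recorded in the CRF and reported to global patient safety in an expedited manner", even when no adverse event occurs. Appendix 4 says "Overdoses without an AE should be reported using the paper SAE Overdose Report form only" and gives no tablet counts.

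The protocol allows two strengths. Participants start on 25 mg tablets, four per dose. If a 150 mg level is added, Section 6.1 states that "50 mg enpatoran tablets and/or matching placebo tablets will be used for Cohort B Part 2 participants enrolled after this implementation", and that "these participants would take, 3 tablets in total per dose administration". Section 4.3 agrees: "The 50 mg tablet strengths may be introduced into Cohort B Part 2 to facilitate doses from 50 to 150 mg". Table 3 makes up the 150 mg dose from three active 50 mg tablets with no placebo tablet.

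**The concern.** A threshold stated in both milligrams and tablets has to agree with itself for every strength in use. This one agrees for 25 mg tablets only. Section 6.7 was not extended to the second strength, and no other visible text supplies counts for 50 mg tablets.

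The count matters because active and placebo tablets look alike (Protocol 6.2), sites are blinded (6.3.2), and compliance is checked partly by counting returned tablets (6.4). A tablet count is therefore a natural working threshold for a site. In a 150 mg arm it errs in the unsafe direction. For an overdose without an adverse event, no adverse event report would draw attention to it, so the threshold alone decides whether an expedited report is sent.

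**Working it through.** **Inputs.** Limits and counts: Protocol 6.7. Strengths, tablets per dose, active/placebo make-up and the 12 ± 2 h dosing interval: Protocol 6.1 and Table 3.

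**1. Reproduce the printed pairs.** Amount = tablets x strength, all tablets active.
- 25 mg: 12 x 25 = 300 mg and 8 x 25 = 200 mg. Both match.

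**2. Same counts with 50 mg tablets, 150 mg arm.**
- 12 x 50 = 600 mg and 8 x 50 = 400 mg, each twice the limit.
- Matching counts: 300/50 = 6 tablets and 200/50 = 4 tablets.

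**3. Size of the gap in the 150 mg arm.** The planned day is 2 x 3 = 6 tablets, or 300 mg.

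| | Lowest intake over the mg limit | Lowest intake over the printed count | Overdose by mg but not by count |
|---|---|---|---|
| 24 hours | 7 tablets, 350 mg | 13 tablets, 650 mg | 7–12 tablets, 350–600 mg |
| Single dose | 5 tablets, 250 mg | 9 tablets, 450 mg | 5–8 tablets, 250–400 mg |

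A doubled dose is 6 x 50 = 300 mg. That exceeds 200 mg, but 6 tablets is below 8. With the day's other dose the total is 9 tablets (450 mg), which exceeds 300 mg but is below 12 tablets.

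**4. Other arms on the three-tablet regimen**, at the planned mix of active and placebo tablets.
- 100 mg arm (2 of 3 active): 12 tablets = 600 x 2/3 = 400 mg; 8 tablets = 400 x 2/3 = 267 mg.
- 50 mg arm (1 of 3 active): 12 tablets = 600/3 = 200 mg; 8 tablets = 400/3 = 133 mg.

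**5. Does a plain conversion to 6 and 4 work?** The single-dose limb does. The 24-hour limb does not. Doses may be 10 hours apart, so doses at 0, 10 and 20 h comply. With 50 mg tablets that is 3 x 3 = 9 tablets, or 450 mg in the 150 mg arm, above 300 mg. With 25 mg tablets it is 3 x 4 = 12 tablets, at most 300 mg, which is not above the limit.

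**6. Was the option used?** Four features of SAP version 4.0 suggest it may not have been:
- Section 9 lists placebo, 25, 50 and 100 mg groups and no 150 mg group.
- Section 13 computes cumulative dose from 25 mg tablets.
- Section 13 divides compliance by 8 tablets per day, so a fully compliant three-tablet participant would score 100 x 6/8 = 75%.
- Section 14.2.4 treats 34 participants as about 10% of planned Cohort B: 34/340 = 10.0%, against 34/432 = 7.9% with the 92 participants reserved for dose adaptation (Protocol 9.2).

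**The case against.** The best reply is that the rule is written in milligrams and the counts are only bracketed equivalents, correct for everyone unless one optional adaptation is made. This stands as a limit on the point: a site that applies the mg limits is not misled by the counts.

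A reader might infer that a blinded site has only the printed count to go on. The documents do not support that. Three tablets per dose instead of four, and 18-unit instead of 24-unit wallets, show which regimen a participant is on. A site can multiply by 50 mg to get the largest possible dose.

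A reader might also infer that overdoses would go undetected. Protocol 6.4 has compliance reviewed at each visit and dosing deviations recorded, so what could be lost is the expedited report, not the record of the event.

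It is also fair to say that operational documents outside this review, such as the CRF guidelines or the Pharmacy Manual, may give counts by strength. The point is therefore confined to the text of 6.7 and the other visible sections.

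Finally, a reader might take the SAP's stage weights, built on 60 + 280 = 340, as showing that the 150 mg arm was never opened. They do not. Protocol 9.1 makes the inverse-normal weights pre-specified, so they would stay the same if participants were added.

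**Conclusion.** The point holds as a minor, conditional inconsistency. The counts in 6.7 are right for 25 mg tablets. If 50 mg tablets are introduced with a 150 mg BID arm, they are twice the mg limits in that arm, and a site using them could miss an expedited overdose report. With 25 mg tablets there is no effect, and no efficacy analysis is touched.

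The conclusion assumes that the 50 mg option is still open and that no unseen site document already corrects the counts. The four SAP features suggest the option may not have been used, but they are inference, not proof.

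A reader might infer that the mg limits are sound as they stand and only the brackets need changing. That goes too far: 300 mg is exactly the planned daily intake at 150 mg BID, and dosing within the permitted interval can exceed it inside 24 hours.

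**What to change.** While the 50 mg option is open, revise 6.7 to:
- give the single-dose limit by strength: above 200 mg means more than 8 x 25 mg or more than 4 x 50 mg tablets;
- give the 24-hour equivalents by strength: 300 mg is 12 x 25 mg or 6 x 50 mg tablets;
- say that blinded tablets are counted as if all were active;
- for the three-tablet regimen, exempt from the 24-hour limit any total made up only of assigned doses taken within the permitted 12 ± 2 h interval.

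Site instructions need the same wording. If the 150 mg option is closed, no change is needed.

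The cost is a short text change and some precautionary reports from lower-dose or placebo participants on three tablets per dose. For example, seven tablets taken off schedule in 24 hours would be reported in every arm, although at the planned mix they are about 7 x 50 x 2/3 = 233 mg in a 100 mg arm, 7 x 50/3 = 117 mg in a 50 mg arm, and nothing on placebo.
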